#### 4.1.3.1.4 *Risk in pregnancy and lactation*

Risks of psilocybin in pregnancy and lactation are unknown. Diphenhydramine is Pregnancy Category B Benzodiazepines are pregnancy category D, with evidence of fetal risk. Use during lactation is considered possibly unsafe. Olanzapine is pregnancy category C, not for use in nursing. Captopril is pregnancy category D, evidence of fetal toxicity. Hydralazine and clonidine are pregnancy category C.

#### 4.1.3.2 *Risks of psychosocial treatments*

There are no known specific risks to META or the preparation and debriefing sessions used in the proposed trial. Non-specific risks include discomfort with sharing personal information, and the risk of therapist misconduct. These risks are judged to be very minor.

#### 4.1.3.3 *Risks of blood draws.*

For most people, needle punctures for blood draws do not cause any serious problems. However, they may cause bleeding, bruising, discomfort, infections and/or pain at the needle site, or dizziness.

#### 4.1.3.4 *Risks of assessment procedures*

There are no known psychological risks associated with the questionnaires used in the study, all of which have been used extensively in clinical populations. It is possible that discussion of substance use and psychiatric symptoms may cause emotional discomfort in some participants. To minimize such discomfort, the following steps will be taken. The consent form will fully inform the participants about the nature of the information to be disclosed in the protocol, and the participants will be informed in the consent form that they can refuse to answer any questions or withdraw from the study at any time. Participants will be informed that all information is confidential. The steps taken to guard confidentiality, as well as the limits to confidentiality, will be described. One of the investigators of the project will be available to meet with any participant who becomes distressed about any aspect of the protocol and wishes to discuss this.

#### 4.1.3.5 *Risks to confidentiality and potential legal consequences.*

Information from this study may be submitted to the U.S. Food and Drug Administration (FDA). Medical records which identify subjects and the consent form signed by subjects may be inspected by the FDA and the local Institutional Review Board. Because of the need to release information to these parties, absolute confidentiality cannot be guaranteed. The results of this research project may be presented at meetings or in publications. However, the identity of individual subjects will not be disclosed in those presentations. Additionally, with the participant's permission, their information may be disclosed to a contact such as a friend or family member that they identify in a written release specifying what information may be shared with whom.

#### 4.1.3.6 *Risks and benefits of alternative treatments.*

Standard of care for outpatient treatment of alcohol dependence is pharmacotherapy with medication monitoring and/or evidence-based psychosocial treatment (individual and/or group therapy). The FDA-approved treatments for alcohol dependence are disulfiram (Antabuse), naltrexone (ReVia and Vivitrol) and acamprosate (Campral). Common side effects of disulfiram include the disulfiram-alcohol reaction, rash, peripheral neuropathy, drowsiness, impotence, headache, acne, and metallic taste. Serious reactions include respiratory depression, cardiovascular collapse, arrhythmias, acute MI, congestive heart failure, seizures, coma, psychosis, optic neuritis, and hepatitis. All but the last three are potential consequences of a severe disulfiram-alcohol reaction. Common side effects of naltrexone include insomnia, nausea, vomiting, anxiety, headache, abdominal pain, muscle aches, rash, dizziness, fatigue, somnolence, anorexia, constipation, liver dysfunction, and chills. Serious reactions include suicidality, depression, precipitated opiate withdrawal syndrome, hypersensitivity reaction, and hepatotoxicity. Common side effects of acamprosate include diarrhea, insomnia, anxiety, depression, asthenia, nausea, pruritus, and dizziness. Serious reactions include suicidality and depression. Evidence-based psychosocial treatments for alcohol dependence include methods based on motivational interviewing (such as the META used in this study), cognitive, behavioral, and cognitive-

behavioral approaches, 12-step facilitation therapies, approaches involving the spouse and family, and standardized counseling approaches incorporating elements of these various approaches.

## 4.2 Adequacy of Protection Against Risks

### 4.2.1 Recruitment and Informed Consent

#### 4.2.1.1 Recruitment

Patients will be recruited from the community through advertisements in local media.

#### 4.2.1.2 Pre-Screening

An IRB-approved pre-screening form will be used by study staff to pre-screen individuals expressing interest in the study, to assess whether they are likely to qualify for the study. Interested participants who pass the pre-screening will be referred for informed consent. No PHI data will be kept unless subjects sign the informed consent form. PHI data of individuals who do not sign an informed consent form will be destroyed. The only information that will be retained from the pre-screening form for individuals that do not pass the pre-screening is the reason they were excluded, the date of the pre-screening, and where they learned about the study.

#### 4.2.1.3 Informed consent process and document

Interested patients will be provided with an informed consent form, approved by the local site's Institutional Review Board and including all pertinent details of the study including description of the following: the assessment interview and questionnaires; the follow-up interviews; description of experimental treatment; risks and benefits of study procedures; alternatives to participation in the study; confidentiality; emergency treatment and compensation for injury; payment for participation; a statement that patients will be informed of any new findings affecting the risks or benefits of the study; a statement that participation is voluntary and that the patient may withdraw at any time; and information about whom to contact with questions or in case of emergency. The consent form will also include a section that allows participants to decide if they would like to participate in any potential future studies related to this study. The consent form will also include assurances of confidentiality and a statement that participation is entirely voluntary, that the decision to participate will in no way influence other aspects of the patient's treatment or involvement in the main trial, and that the participant is free to withdraw participation at any time. Prior to signing the informed consent document, patients will be required to pass an informed consent quiz (10 items, passing score 90% or above) covering key elements of the study. Patients who score less than 90% on the informed consent quiz will be counseled further and will have up to a total of 3 chances to pass the quiz. Patients indicate their consent to participate in the study by signing and returning the informed consent form.

### 4.2.2 Protection Against Risk

#### 4.2.2.1 Management of risk due to study treatments

Risks of hallucinogen administration are thought to be minimized by a) careful screening of participants, b) extensive preparation, c) establishment of rapport and trust between participants and monitors, d) presence of two monitors during the psilocybin sessions, e) a safe and reassuring physical environment, f) careful planning for unusual but potentially serious adverse reactions, and g) debriefing and follow-up for possible residual adverse effects [105]. These principles are incorporated into our protocol as follows.

*a. Subject selection:* Exclusion criteria are designed to exclude patients who would be at elevated risk for adverse events due to psilocybin. These criteria are listed in Section 3 above, and include both medical exclusions and psychiatric exclusions for serious psychopathology, history of violent or suicidal behavior, and family history of psychosis or suicide.

*b. Subject preparation:* In addition to the information and discussion provided in the informed consent process, participants will spend a total of 6 hours in 4 sessions: two 1-hour META sessions, and two preparation sessions (4 hours total) including both the PSI therapist and the META therapist. Both of the clinicians will be present during the psilocybin sessions. Preparation will include 1) open-ended questions to establish rapport, learn about the participant's history, belief system, and values, assess motivation and expectations for the

study, and discuss any previous experience with hallucinogens; 2) detailed information about the physiological and psychological effects of psilocybin; 3) emphasis that the purpose of the psilocybin sessions is to facilitate behavior change, and discussion of how this could work; 4) advice as to how to deal with dysphoric reactions to psilocybin, should they occur; 5) identification of any personally meaningful items that the participant will bring to the session (e.g., photographs, images, objects of personal or religious significance); and 6) discussion of ground rules for the session.

*c. Establishment of rapport and trust:* The extensive contact between the participant and therapists prior to the psilocybin sessions is intended to build rapport and trust during the psilocybin sessions.

*d. Support during psilocybin sessions:* Because this study involves use of psilocybin in a clinical population as part of an intervention intended to be therapeutic, the two study therapists will serve as the monitors who will attend the patient during the psilocybin sessions. At least one of these therapists will be a licensed clinician.

*e. Physical environment:* The psilocybin session will take place in outpatient facilities that are appropriate for hallucinogen administration sessions. To the extent possible, the room used for the session will be specially prepared for the sessions to provide a warm and home-like rather than a stark clinical quality because of the large influence that setting can have on the subjective effects of hallucinogens. Each site will have detailed SOPs in place for managing medical or psychiatric emergencies should any occur.

*f. Planning for emergencies:* Each of the research sites has established practices for managing medical and psychiatric emergencies, and the study staff will continue to utilize these procedures. Staff will be responsible for monitoring participants for possible clinical deterioration or other problems, and for implementing appropriate courses of action. Acute adverse reactions to psilocybin initially will be managed by increasing psychological support ("talking down"). Medications will be available for administration if needed to treat hypertension (sublingual captopril 25 mg orally/sublingually, clonidine 0.1 mg PO, and hydralazine 10 mg PO), anxiety (diazepam 5-10 mg PO, or lorazepam 1 mg IM), or acute psychosis posing a danger to the participant or others (olanzapine 5-10 mg PO or IM). Referral for emergency treatment and/or hospitalization will be available at each site. A study clinician will be available by pager or phone at all times during study participation.

*g. Debriefing and Follow-up:* Debriefing sessions, approximately 2 hours long and conducted by the PSI therapist and the META therapist on the day after the psilocybin sessions, consist of the following elements: 1) open-ended inquiry concerning the psilocybin session (and what has happened since); 2) invitation to reflect on the experience; 3) discussion of what has changed as a result of the session; 4) discussion of how the session has affected the participant's relationship to alcohol; and 5) assessment of mental status. Additional META sessions and booster sessions (two 1-hour sessions following the first debriefing session, and three 1-hour sessions following the second debriefing session) will allow further opportunity to process the experience.

#### 4.2.2.2 Minimization of risk to confidentiality

Confidentiality of research material will be ensured by storing the research materials in locked cabinets in NYU space within the A, C-D, and H buildings of Bellevue Hospital Center. Material will be available only to project staff, and only as needed. All project staff will be thoroughly trained in issues relating to confidentiality.

Participants will be identified in case report forms (CRFs) by initials and an identification code. Data will be entered into REDCap™, a program designed specifically to protect patient privacy and confidentiality (see section 3.3.11). Published reports will be based on group data; no individual data will be reported. As a further protection to confidentiality, we will request a Confidentiality Certificate from the Department of Health and Human Services (DHHS). With this Certificate, the investigators cannot be forced (for example by court order or subpoena) to disclose research information that may identify individual patients in any Federal, State, or local civil, criminal, administrative, legislative, or other proceedings. Disclosure will be necessary, however, upon request of DHHS for audit or program evaluation purposes. DHHS ensures confidentiality of requested data. Participants will be notified in the informed consent that the Certificate of Confidentiality does not prevent them or a member of their family from voluntarily releasing information about themselves and their involvement in the research. If an insurer, employer or other person obtains their written consent to receive research information, then the researcher may not use the Certificate to withhold that information. Participants will also

be informed that the Certificate of Confidentiality does not prevent the researchers from disclosing voluntarily, without their consent, information that would identify them as a participant of the research project under the following circumstances: the present danger of child abuse, suicide, and/or homicide. In addition to current measures, the present study will comply with the Health Insurance Portability and Accountability Act of 1996. Records related to this study will not be released to third parties.

### **4.3 Potential Benefits of the Proposed Research to Human Subjects and Others**

#### **4.3.1 Potential Benefits to Participants**

Participants may or may not experience clinical benefit from this study. There is equipoise regarding the effects of the experimental drug used in this study. Aspects of study participation likely to be beneficial include free medical and psychiatric evaluations, the attention and support of participating in a clinical trial, and a course of an evidence-based psychosocial treatment for alcohol dependence.

#### **4.3.2 Potential Benefits to Others.**

Knowledge gained through this study may aid the development of more effective treatments for individuals with alcohol dependence and other addictive disorders.

#### **4.3.3 Risk Benefit Assessment**

Risks to individual participants appear to be balanced by the likely benefits of study participation, and outweighed by the potential benefits to others.

### **4.4 Importance of the Knowledge to be Gained**

There is an urgent need to develop more effective methods to help people who suffer from addictions and other forms of loss of behavioral control (e.g., overeating). The knowledge gained through this study could point the way to an entirely new treatment for alcohol dependence, and may also yield important gains in understanding of the psychological processes that underlie behavior change. As indicated above, these potential benefits (in addition to the potential benefits to individual participants) appear to justify the risks to individual participants.

### **4.5 Data and Safety Monitoring Plan**

#### **4.5.1 General Considerations**

Although the safety profile of psilocybin in clinical research is well established, our pilot study is the only controlled trial to date using psilocybin in an alcohol dependent population (although there are more than thirty published studies reporting on the use of LSD in the treatment of alcohol dependence). The data and safety monitoring plan is therefore designed both to ensure that the risks of medications and study-related procedures are minimized for patients, and to minimize any doubt that there are adequate safeguards in place to minimize this risk.

#### **4.5.2 Institutional Review Board (IRB)**

All study procedures will be approved by the local IRB at each participating site.

#### **4.5.3 Data and Safety Monitoring Board**

A Data and Safety Monitoring Board (DSMB) will be established, comprising three to five individuals appointed by the Heffter Research Institute. This committee will meet (in person or by teleconference) prior to enrollment of the first participant in the double blind and at least annually thereafter, including meetings after enrollment of the first 10 participants, and upon completion of stage 1 and stage 2 of the trial. At its meetings the Board will

- review protocol violations and deviations to assess adequacy of study
- ensure documentation of informed consent
- review enrollment and retention
- review IND information
- discuss investigator or key personnel changes

- review completeness and quality of data collection forms
- evaluate the aggregate analysis of adverse events/serious adverse events
- review confidentiality
- review interim analyses conducted at completion of stage 1 and stage 2 of the trial.

Following each meeting, the board will provide the PI with a report including a recommendation to continue the study unchanged, continue with modifications of the protocol and/or the consent form to protect participant safety, or terminate the study.

#### **4.5.4 Procedures for Monitoring and Reporting Adverse Events.**

The study staff will be trained to monitor for and report adverse events and Serious Adverse Events. Adverse events (AEs), when present, will be collected on an AE case report form at the end of the first psilocybin session and at all subsequent visits. The form will include an assessment of clinical significance and study relatedness. Serious Adverse Events (SAEs) will be documented on a separate SAE form. AEs will be reported in accordance with federal law and policies the IRB requirements. Reporting procedures vary depending on the severity of the AE.

##### **4.5.4.1 Safety reporting to the FDA**

Safety reporting will follow 21CFR312.32. Site investigators will notify the Lead Investigator of any SAEs within 24 hours of becoming aware of the event. The Sponsor will notify the FDA regarding any suspected adverse reaction associated with the use of the drug that is both serious and unexpected. The sponsor will also notify the FDA of findings from other human, animal, or in vitro studies that suggest increased risk to humans, or any pattern of increase in the rate of adverse events over what is expected. Each notification will be made as soon as possible and no greater than 15 calendar days after the initial receipt of the information. Each written notification will be submitted on an FDA Form 3500A. The Principal Investigator will also notify the FDA of any unexpected fatal or life-threatening experience associated with the use of the drug as soon as possible but no later than 7 calendar days after the initial receipt of the information.

##### **4.5.4.2 Other reporting to FDA**

On an annual basis as part of the update to the study IND, the Principal Investigator will submit to the FDA:

A summary of all IND safety reports submitted during the past year.

A list of all subjects who died during the participation in the investigation, listing cause of death for each.

A list of subjects who dropped out during the course of the investigation in association with any adverse experience, whether or not thought to be drug related.

##### **4.5.4.3 Stopping Rules for Study**

Stopping rules will be put in place if 1) there are untoward and concerning levels of Adverse Event (AE) or Serious Adverse Event (SAE) outcomes attributable to psilocybin, or 2) there is a significant worsening of drinking behavior or consequences in the psilocybin group. The methodology that will be used for both of the 2 rules above will be as follows: interim analyses will be performed in the aggregate (psilocybin and control groups combined) for both AEs/SAEs and drinking clinical outcomes, and these results will be reviewed by the DSMB. If the aggregate analyses reveal either concerning levels of AEs/SAEs or worsening drinking outcomes, then an unblinded statistician will analyze the data to determine (as best as possible from the data) if the concerning AEs/SAEs and/or the worsening drinking outcomes are significantly due to the psilocybin group compared to the placebo. If the DSMB finds it is likely the psilocybin group is contributing to negative outcomes, they will consider solutions including protocol changes or potentially stopping the study.

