### 3.3.12.3.2 Method

For PHDD we will employ a MMRM including fixed, categorical effects of treatment, assessment, and site; site-by-treatment and treatment-by-assessment interactions; the continuous, a fixed covariate (week 1-4 PHDD); and using monthly values of PHDD (weeks 5-8, 9-12, 13-16, 17-20, 21-24, 25-28, 29-32, 32-36) as the dependent measure. Site and the site-by-treatment interaction will be removed from the final model if not significant at the  $p < 0.05$  level. Secondary drinking measures with a continuous scale of measurement, i.e., PDA and DPDD, will be tested in a similar fashion and for days to first drinking day and days to first heavy drinking day (5 or more standard drinks for a man, 4 or more standard drinks for a woman). Cox survival analysis will be used. Measures of effect size will be calculated for all planned between-group contrasts (Hedges  $d$ ) and the  $Q$  statistic will be calculated to assess the homogeneity of effect across the primary and secondary outcome measures of drinking.

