#### **3.3.13 Study Milestones**

We propose to implement the study in three stages, with interim analyses and DSMB review after the first and second stages.

Stage 1: Following final protocol approval by all necessary authorities and procurement of necessary funding, staff will be trained, at least 4 pilot/training participants per site will be treated, and 20 participants will be randomized into the main trial across two sites (UNM and NYU, 10 per site). At the end of this stage, feasibility and tolerability will be assessed, and necessary protocol modifications may be made.

Stage 2: An additional 80 participants will be randomized, with the possible addition of one or two additional sites to enhance recruitment capacity. At the end of this stage, interim checks of attrition rates and the assumed error standard deviation  $\sigma$  for the primary outcome measure will be conducted to assess the adequacy of the projected study sample size. This check will be performed by an unblinded statistician, who will estimate the primary model, and report back on error variance and drop-out rates. Additional necessary protocol modifications may be made, and final sample size will be determined. In addition, safety interim looks will be performed (without formal statistical testing) at the regular DSMB meetings or unscheduled times per the DSMB's request. Although at this time we are not planning a formal statistical interim analysis for efficacy or futility, such an interim analysis can be performed if requested by the DSMB or the sponsor.

Stage 3: Assuming 180 participants are required, the 80 remaining participants will be randomized, with an additional 9 months to complete treatment and assessment of the final participants.

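### The drinking-harm stopping rule targets the psilocybin arm but reaches a by-arm analysis only through a pooled screen, which can hide worsening on psilocybin if controls improve

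*Combined protocol and SAP*

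**What the plan says.** Section 4.5.4.3 (Stopping Rules for Study) has two criteria. The second applies if "there is a significant worsening of drinking behavior or consequences in the psilocybin group", so its target is one arm. A single method then serves both criteria: "The methodology that will be used for both of the 2 rules above will be as follows", and what follows is that "interim analyses will be performed in the aggregate (psilocybin and control groups combined) for both AEs/SAEs and drinking clinical outcomes". The by-arm step is conditional: "If the aggregate analyses reveal either concerning levels of AEs/SAEs or worsening drinking outcomes, then an unblinded statistician will analyze the data". The section gives no drinking measure, reference period, size of worsening or significance level for the pooled step.

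Three other places bear on this:

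- Section 4.5.3 lists among the DSMB's tasks to "evaluate the aggregate analysis of adverse events/serious adverse events".
- Section 3.3.13 says that "safety interim looks will be performed (without formal statistical testing) at the regular DSMB meetings", or at other times if the DSMB asks. It does not say whether these looks are by arm. It also allows a formal efficacy or futility interim on request. Its Stage 2 check uses an unblinded statistician "who will estimate the primary model, and report back on error variance and drop-out rates"; no arm-level drinking result is reported.
- Section 3.3.12 refers to a separate SAP for the full analyses. That SAP was not available for this review.

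**The concern.** The rule looks for harm in one arm with a statistic that averages that arm with the other. Both arms receive the same psychosocial treatment, so some improvement among controls is plausible, and any improvement offsets worsening on psilocybin in a pooled mean. If the offset is large enough, the pooled result is not concerning and the rule as written does not call for the by-arm comparison.

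At stake is whether the DSMB is given the comparison that the rule is about. Section 4.5.4.3 is the only place that provides for a by-arm look at drinking for harm, and it places that look behind the pooled screen.

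**Working it through.** **No figure to reproduce.** Section 4.5.4.3 states no threshold, alpha or boundary. What follows is arithmetic on the allocation ratio, then an illustration on stated assumptions.

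**Inputs from the protocol.** Allocation is 1:1, 90 per group (section 3.3.1). Stage 1 randomises 20 main-trial participants and Stage 2 a further 80 (section 3.3.13), so 20 + 80 = 100, or about 50 per arm, at the end of Stage 2. The only evidence on change with therapy alone is the pilot report of a modest change over the first month of psychosocial treatment (section 3.3.3.2), with no size given.

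**Assumptions.** Within-arm SD of change = 1, and all 100 participants have outcome data. Changes are in SD units, with + meaning worse. The screen is the pooled mean change and its informal trigger is any pooled worsening. The between-arm test is a t test at one-sided 2.5%.

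**Step 1, masking.** With psilocybin change dp and control change dc, the pooled mean is m = (dp + dc)/2. If dc = 0 the signal is halved. If dc = -dp it is zero. If controls improve by more than psilocybin worsens, the pooled result looks like improvement.

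**Step 2, detection at 50 per arm.**

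- Screen fires: Phi(m x sqrt(100)) = Phi(10m).
- Between-arm test: noncentral t, df 98, noncentrality (dp - dc) x sqrt(50/2) = 5(dp - dc).
- With equal n and equal variance, the sum and the difference of the arm means are independent, so two-step rule = screen x between-arm test.

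Worked case, dp = +0.3 and dc = -0.2: m = 0.05, the screen is Phi(0.5) = 0.691, the between-arm test (noncentrality 2.5) is 0.697, and the product is 0.48.

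Psilocybin fixed at +0.5 SD (the between-arm gap grows down the table):

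| Control change | Screen | Direct by-arm test | Two-step rule |
|---|---|---|---|
| +0.2 | >0.999 | 0.32 | 0.32 |
| 0 | 0.99 | 0.70 | 0.69 |
| -0.2 | 0.93 | 0.93 | 0.87 |
| -0.3 | 0.84 | 0.98 | 0.82 |
| -0.5 | 0.50 | 0.999 | 0.50 |

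Between-arm gap held at 0.5 SD, which isolates the cost of the pooled step:

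| Psilocybin / control | Screen | Direct by-arm test | Two-step rule |
|---|---|---|---|
| +0.5 / 0 | 0.99 | 0.70 | 0.69 |
| +0.3 / -0.2 | 0.69 | 0.70 | 0.48 |
| +0.25 / -0.25 | 0.50 | 0.70 | 0.35 |

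This trigger also fires half the time when neither arm changes, since Phi(0) = 0.50.

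**Step 3, Stage 1.** At 10 per arm with psilocybin at +0.5 SD, the direct by-arm test reaches only 0.18, 0.32, 0.40 and 0.56 for controls at 0, -0.2, -0.3 and -0.5 SD. Neither approach is reliable there.

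**Step 4, adverse events.** With 50 per arm and a Fisher test between arms, adding the pooled screen leaves power at 0.19 for 10% v 2% (one-sided 2.5%; screen at 6 or more events in 100). Power falls from 0.66 to 0.59 for 20% v 5% (one-sided 5%; screen at 10 or more in 100). The effect is minor.

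**Step 5, reference period.** The choice affects which row applies. Against pre-treatment drinking, a fall in both arms is plausible: entry requires at least 4 heavy drinking days in 30 (section 3.3.6.1), and four therapy sessions precede randomisation (Figure 2). Against weeks 1-4, the covariate in the primary model (section 3.3.12.3.2), a rise in both arms is plausible. That period already contains the therapy and the week of attempted abstinence before the first session (section 3.3.8.1.3).

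**The case against.** The case for leaving the rule alone has several parts.

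- **The trigger is loose.** The pooled step asks only for concerning levels or worsening, and section 3.3.13 says its safety looks involve no formal testing. A reader might assume a one-sided 2.5% pooled test and conclude that the rule would usually miss harm: with psilocybin at +0.5 SD, such a screen alone would fire with probability 0.29 or 0.15 when controls improve by 0.2 or 0.3 SD. The documents state no such test, so those figures do not describe this plan. This objection stands, and the tables above use the informal trigger.
- **Controls may not improve.** The pilot's modest change came in the first month of therapy, which a weeks 1-4 reference would largely absorb, and nothing in the documents supports a control improvement of 0.3 to 0.5 SD. This stands as a limit on size. It does not reverse the point: with controls at +0.2 SD the two-step rule and the direct test are level (0.317 v 0.318), and removing the pooled step never lowers by-arm detection.
- **Other routes exist.** A reader might infer that the DSMB is barred from arm-level data. The documents do not say so. Section 3.3.13 lets it request looks or a formal interim, section 4.5.3 lets it recommend modification or termination, and section 4.2.2.1 makes staff watch for individual deterioration. The word aggregate in section 4.5.3 is not defined there and may mean cumulative. Still, none of these requires a by-arm drinking comparison.
- **Adverse events.** A reader might extend the concern to AEs and SAEs with equal force. Relatedness ratings (sections 3.3.10.9 and 4.5.4), SAE notification within 24 hours (section 4.5.4.1) and the small losses in Step 4 argue against that.
- **Pooled review protects the trial.** It limits exposure to arm-level primary-outcome data. This is a real cost of the change, and a harm-only label reduces it but does not remove it.

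**Conclusion.** The point holds as a conditional weakness. Followed as written, section 4.5.4.3 can miss its own target: worsening on psilocybin is partly hidden in a pooled mean when controls improve, and fully hidden when they improve at least as much as psilocybin worsens. If controls are unchanged or worsen, an informal pooled trigger costs almost nothing.

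For a fixed between-arm gap of 0.5 SD at the end of Stage 2, detection falls from 0.70 to between 0.69 and 0.35, depending on how the gap divides between the arms. This rests on 50 per arm with complete data, a mean-change screen, any pooled worsening as trigger, and a one-sided 2.5% between-arm test. The protocol states none of the last three, and it gives no SD or control change, so the size is illustrative. The gain from a direct look is mainly at Stage 2.

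This is a cheap improvement to the monitoring text, held with medium confidence because the separate SAP may already close the gap.

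**What to change.** In section 4.5.4.3, and consistently in sections 3.3.13 and 4.5.3:

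1. Remove the pooled result as a precondition for the by-arm analysis.
2. State that at DSMB meetings the unblinded statistician supplies closed-session tables of drinking outcomes, AEs and SAEs by coded arm, for harm review only. Investigators stay blinded, and any efficacy interim is handled separately.
3. State the reference period against which worsening is judged.
4. Leave thresholds to the DSMB.

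If the SAP already specifies by-arm tables for the DSMB, a cross-reference in section 4.5.4.3 is enough.

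The cost is wording in three sections plus tables from a statistician and a DSMB already in the plan. The sample size does not change. The downside is that the DSMB sees arm-level data on the primary outcome, percent heavy drinking days, which pooled review avoids.
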